H1a: PTSD will be associated with increased systemic levels of IL-1b, TNF- α and IL-6. H1b: WTC workers with asthma and PTSD will have an increased expression of sputum neutrophilia and IL-6 levels. H1c: Increased sputum neutrophilia and higher IL-6 levels will be associated with poorer disease control among WTC workers with asthma.

2. Examine the longitudinal association between PTSD and symptom perception in WTC workers with asthma

H2a: WTC rescue and recovery workers with PTSD will be more likely to over-perceive asthma symptoms in naturalistic settings compared to participants without PTSD. H2b: Associations between subjective (Asthma Control Questionnaire, use of rescue medications, and Asthma Quality of Life Questionnaire scores) and objective (forced expiratory volume in 1 second [FEV₁]) measures of asthma control will be weaker among WTC workers with PTSD than those without PTSD.

3. Assess the relationship between PTSD and adherence to asthma SMB (medication adherence, trigger avoidance, and inhaler technique) in WTC workers and identify the pathways linking them

H3a: PTSD is associated with lower adherence to SMB among WTC workers with asthma. H3b: Asthma (identity, timeline, and cause), medication beliefs (necessity and concerns about controller medications), and over-perception of symptoms will mediate, in part, the influence of PTSD on SMB.

4. Develop and pilot test an integrated intervention for asthma and PTSD by adapting the Relaxation Response Resiliency Program (3RP), a mind-body program, with counseling to promote asthma SMB, and education to correct over-perception of asthma symptoms

H4: The intervention will be acceptable to WTC workers, change beliefs about asthma, correct symptom over-perception, improve asthma medication adherence and quality of life and reduce symptoms of PTSD. We are currently seeking approval for the observational portion of the study only. We will request IRB approval for the interventional (pilot) phase at a later date, in advance of commencing the pilot.

2) Background

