Asthma Symptom Perception: We will use the AM2 computerized peak flow monitor (ERT Corporation, Philadelphia, PA; Figure 2) to assess symptom perception by comparing actual and perceived PEF values for 4 weeks following the baseline, 6- and 12-months interviews.^{77,109,184} Following a well validated protocol, RAs will train participants to enter the PEF estimate (step 1) and then perform the PEF effort (step 2). To help them estimate their PEF, the RA will attach a colored sticker to the AM2 showing the participant's predicted PEF values (based on age, sex and height) that correspond to the go (green), caution (yellow), and danger (red) zones of asthma control (Figure 3).¹⁷² After entering their estimated PEF, participants will perform 3 maximal effort blows, with 2 minute rests between each. The actual peak flow values of each blow will not appear on the device. The AM2's acoustic alarm will remind them to use it in the morning and evening.

	Protocol Title:	Assessing Inflammatory and Behavioral Pathways Linking PTSD to Increased Asthma Morbidity in WTC Workers
	Principal Investigator Name/Contact Info:	[name], DrPH [contact]; [contact]
	Primary Contact Name/Contact Info	[name], MS [contact]; [contact]
	Date Revised:	07/25/16
	Study Number:	IF# 1896970; GCO# 16-0945

The asthma risk grid (Figure 4) was developed to quantify symptom perception accuracy.^{77,109,172,184,185} Each objective PEF is plotted against the corresponding subjective estimate of PEF to generate a percent of objective personal best. Patients' estimates are categorized in the *accurate*, *under-perception*, and *over-perception* zones, and must be at least 10% higher or lower than the actual PEF value (to ensure that estimates close to the accurate zone are not classified as inaccurate) to be considered in these zones, respectively. Each participant's symptom perception will be characterized as the percent of time they spend within each perception zone. The percentage of estimates in the over-perception one will be the main study measure. Home Peak Flow Meter (PFM) use: We will ask patients with their own PFM's not to use them while they are using the AM2. In our prior studies, <5% of participants used a PFM ≥ 1 time/week.

Figure 2: AM2 Peak Flow Meter

Figure 3. AM2 Sticker to Help Patients Estimate their PEF

[figure not shown]
[figure not shown]

Figure 4. Asthma Risk Grid

C. Asthma SMB: will be based on NIH guidelines.¹⁷² Asthma Controller Medication Adherence:

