Subjective Measures: Asthma Symptoms: Asthma control will be assessed with the Asthma Control Questionnaire (ACQ).^{197,198} It is available in English and Spanish and has excellent validity. Use of Beta2-agonists: Over-perception may be associated with increased use of quick relievers. Thus, we will use self-reports as well as Doser devices to objectively capture use of these medications for 4 weeks after each interview. Acute Resource Utilization: will include self-reported and electronic data on unscheduled office and ED visits and asthma-related hospitalizations. We will identify visits occurring at outside institutions by self-report and request external records. Although resource utilization can be considered a more objective measure it also is influenced by subjective perceptions concerning the need to seek help. Asthma quality of life: We will use the validated Mini Asthma Quality of Life Questionnaire (AQLQ); available in English and Spanish.¹⁹⁹

Independent Variables (Table): PTSD: Structured Clinical Interview (SCID): The SCID is considered the gold-standard psychiatric interview.²⁰⁰ The Bilingual version of the SCID will be used at the baseline, 6- and 12-month visits as the semi-structured psychiatric interview.²⁰⁰⁻²⁰² A psychology graduate student or social worker will administer the PTSD and the mood disorders modules. [name] and [name] will provide supervision for all diagnostic issues. Quality Assurance: We will randomly select 10% of audiotaped recordings for Drs. [name] or [name] to rate for accuracy and to provide feedback to interviewers. Patient Safety: If patients with active suicidal ideation are identified, the PIs will be notified to determine the need for an emergency psychiatric consult. Participants with PTSD will be given a list of counseling sites. Additionally, we will ask for patients' consent (signed HIPAA authorization) to alert their physicians about the SCID results after a lag of 4-6 weeks (to be able to assess the impact of PTSD on symptom perception and SMB). We will collect detailed data on medications for PTSD and/or depression by self-report and EMR review.

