Sputum Neutrophilia	0.25	0.30	106
Sputum Eosinophilia	0.50	0.25	107
IL-6, pg/ml	4 (2)	2	67

 Mount Sinai	Protocol Title:	Assessing Inflammatory and Behavioral Pathways Linking PTSD to Increased Asthma Morbidity in WTC Workers
	Principal Investigator Name/Contact Info:	[name], DrPH [contact]; [contact]
	Primary Contact Name/Contact Info	[name], MS [contact]; [contact]
	Date Revised:	07/25/16
	Study Number:	IF# 1896970; GCO# 16-0945

Power Calculations: Assumptions about the expected retention rate ($\geq 80\%$), the prevalence of PTSD ($\sim 30\%$) and the distribution of inflammatory markers were derived from our preliminary data and the literature.^{1,7,8} Under these assumptions, with 175 participants undergoing sputum induction, the study will be powered to test Aim 1 hypotheses (Table 3).

Aim 2. Examine the longitudinal association between PTSD and symptom perception in WTC workers with asthma: We will calculate the proportion of blows that each participant over-estimate using AM2 data. A probit transformation will be applied to normalize the proportion of over-perceived guesses; differences in the distribution of the transformed variable at each time point in participants with and without PTSD will be assessed with a t-test.²²⁷ We will use a GEE model to assess the association between PTSD and symptom perception over time.²²⁸ We will then fit a fixed effects model (i.e., limited to within subject variability) to assess the longitudinal effect of changes in PTSD symptoms (PCL scores) on symptom perception. We will repeat these analyses adjusting for potential confounders as described above.

[figure not shown]
We will also assess the correlation between subjective (ACQ scores, use of beta2-agonists, AQLQ scores) and objective (FEV₁) measures of morbidity separately in asthmatics with and without PTSD and apply a Fisher's z' transformation to assess if the association varies between these groups. Then, we will fit a GEE model with ACQ scores (or use of beta2-agonists/AQLQ) as the dependent variable and as predictors, FEV₁, PTSD status, and an interaction between PTSD and FEV₁. In this model, the interaction term will test whether the association between objective and subjective measures varies according to the participant's PTSD status.

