Training and Fidelity: Masters-level clinicians will be trained to deliver the adapted 3RP intervention by [name]. [name] will provide weekly supervision and review audio-taped sessions for treatment fidelity. Pilot RCT Procedures: [name] will adapt the 3RP procedural manual to incorporate new components. We will use data from the 12-month interview to identify WTC workers with asthma and PTSD for the pilot (N=60). Eligible WTC workers who agree to participate will be randomized 1:1 (using adaptive randomization to balance the number of participants in each arm with respect to age, sex and PTSD symptoms severity) to the intervention vs. an attention control group.

Intervention Group: Participants randomized to the adapted 3RP condition will participate in the manualized 8-session group -based program (4-8 participants per group). They will also receive an unblinded AM2 device during the first 6 weeks of the intervention. Attention Control: Control patients will participate in an 8-session group-based program of similar time and therapist attention. The control intervention will consist of educational sessions covering general asthma knowledge (Asthma 1-2-3)²³⁹ group-based support. They will receive blinded AM2 devices.

Outcome Assessment: A telephone follow-up survey 4 weeks after the last session will be administered to assess the patient’s illness and medication beliefs, anxiety sensitivity, their adherence to asthma SMB, and PTSD symptoms. Data Analysis: 1) Quantitative Assessment: Differences in illness (B-IPQ), medication beliefs (BMQ), anxiety sensitivity (ASI-3), adherence to asthma medications (MARS), and PTSD symptoms (PCL) will be assessed using a t-test

 Mount Sinai	Protocol Title:	Assessing Inflammatory and Behavioral Pathways Linking PTSD to Increased Asthma Morbidity in WTC Workers
	Principal Investigator Name/Contact Info:	[name], DrPH [contact]; [contact]
	Primary Contact Name/Contact Info	[name], MS [contact]; [contact]
	Date Revised:	07/25/16
	Study Number:	IF# 1896970; GCO# 16-0945

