If selected to participate in the pilot study, subjects may receive up to \$160 for their participation in this pilot. Upon completing the pilot study baseline interview they will receive \$70 for their time and effort. Upon completing the follow-up interview for the pilot study they will receive \$20 for their time and effort. This will be given to them at the end of the study in cash unless otherwise requested. At their completion of the pilot study, they will receive \$70 for your time and effort.

Research Interview	Payment
Observational Study	
Baseline Interview	\$50
Follow-up Phone call after baseline	\$10
1-month interview (including sputum test)	\$90
Return of electronic monitoring devices (from baseline) in person	\$10
6-month Interview	\$50
Return of electronic monitoring devices (from 6-month interview) by mail	\$10
12-month Interview	\$50
Return of electronic monitoring devices (from 12-month interview) by mail	\$10
Total (Observational Study)	\$280
Pilot Study	
Pilot Baseline	\$70
Follow-up Phone Interview	\$20
End of Study	\$70
Total (Pilot Study)	\$160

11) Consent Process

Setting:

Consent will take place in a private room in the outpatient clinics of the Pulmonary or General Internal Medicine (IMA) Departments at Mount Sinai Hospital.

Process:

Only members of the research team who have been fully trained in the protocol will obtain the treating provider's permission to recruit potential patients.

	Protocol Title:	Assessing Inflammatory and Behavioral Pathways Linking PTSD to Increased Asthma Morbidity in WTC Workers
	Principal Investigator Name/Contact Info:	[name], DrPH [contact]; [contact]
	Primary Contact Name/Contact Info	[name], MS [contact]; [contact]
	Date Revised:	07/25/16
	Study Number:	IF# 1896970; GCO# 16-0945

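### The pilot RCT's only quantitative test ignores the baseline score and the factors its allocation balances, and two effects claimed in H4 are not among its listed outcomes

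*Combined protocol and SAP*

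**What the plan says.** All references are to the combined protocol and SAP.

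- **Allocation** (Aim 4, Pilot RCT Procedures): 60 workers are randomised 1:1 by an adaptive scheme that balances the arms "with respect to age, sex and PTSD symptoms severity".
- **Baseline contact** (section 10, Payment to Subjects): "Upon completing the pilot study baseline interview they will receive" a payment. The content of that interview is not described.
- **Outcome contact** (Aim 4, Outcome Assessment): "A telephone follow-up survey 4 weeks after the last session will be administered to assess" beliefs, anxiety sensitivity, self-management and PTSD symptoms.
- **Analysis** (Aim 4, Data Analysis): differences in B-IPQ, BMQ, ASI-3, MARS "and PTSD symptoms (PCL) will be assessed using a t-test" or a Wilcoxon test. No covariate is named, and the differences are not defined as follow-up scores or changes from baseline.
- **Power** (Aim 4): more than 80% for clinically meaningful differences on these instruments with 30 per arm. No difference, SD or alpha is given.
- **Claims** (section 1, H4): the intervention will, among other things, "correct symptom over-perception, improve asthma medication adherence and quality of life and reduce symptoms of PTSD".
- **Cohort tools for the two unlisted effects** (section f; Aim 2): the Mini AQLQ for quality of life. For over-perception, "The percentage of estimates in the over-perception one will be the main study measure", and in the Aim 2 analysis "A probit transformation will be applied to normalize the proportion of over-perceived guesses".

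**The concern.** A design that balances on prognostic factors and interviews participants before treatment has the material for an adjusted comparison. With 30 per arm, that is the cheapest precision available. An unadjusted test leaves it unused. If the test were applied to change scores, it would be less precise than a plain follow-up comparison whenever the baseline correlation is below 0.5.

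H4 also names effects that the pilot's outcome and analysis text does not pick up. Followed as written, the pilot could finish with no prespecified comparison for quality of life or over-perception, although the cohort already has an instrument for each.

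**Working it through.** **Inputs.** From the documents: 30 per arm, power above 80%, and the balancing factors. Assumed because not given: two-sided 5%; r, the correlation of each score with its own baseline, at 0.3, 0.5 and 0.7; no session-group effect.

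**Step 1, the plan's figure.** It cannot be reproduced without a difference, so it is inverted. By normal approximation, d = (1.960 + 0.842) × √(2/30) = 0.72. By noncentral t with 58 df, d = 0.736. The power statement therefore holds only for differences of about 0.74 SD or more. At 0.5 SD the t-test has 48% power.

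**Step 2, three analyses.** The variance of the arm difference is 2σ²/30 times:
- follow-up scores: 1 (58 df);
- change scores: 2(1 − r) (58 df);
- ANCOVA: 1 − r² (60 − 2 − 4 = 54 df, with age, sex and PCL assumed to explain nothing further).

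For example, ANCOVA at r = 0.5 gives 0.72 × √0.75 ≈ 0.63 by normal approximation and 0.64 by noncentral t.

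| | r = 0.3 | r = 0.5 | r = 0.7 |
|---|---|---|---|
| Detectable d, follow-up scores | 0.74 | 0.74 | 0.74 |
| Detectable d, change scores | 0.87 | 0.74 | 0.57 |
| Detectable d, ANCOVA | 0.70 | 0.64 | 0.53 |
| t-test power at the ANCOVA d | 76% | 68% | 52% |
| n per arm for the t-test to reach 80% there | 33 | 40 | 58 |

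**Step 3, worst case for ANCOVA.** Suppose age, sex and PCL carry no information and all four covariates are left to chance. The expected variance inflation is (60 − 3)/(60 − 3 − 4) = 57/53 = 1.075, so detectable d rises by √1.075 = 1.037, to 0.73, 0.66 and 0.55. Power at d = 0.736 is then about 81%, 88% and 97%, against 80% unadjusted. At r = 0.3 there is essentially no gain.

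**Step 4, error rate after balanced allocation.** Minimisation on age, sex and baseline severity was simulated with 60 participants, a biased coin of 0.8 and 3,000 runs per r. Here r is the correlation of the outcome with the balanced severity score, which fits the PCL most directly. Type I error of the unadjusted t-test was 0.040, 0.032 and 0.017; for ANCOVA it was 0.042, 0.050 and 0.050. With simulation error of about 0.004, the two tests are indistinguishable at r = 0.3, and the t-test is clearly conservative at 0.5 and 0.7. Power at d = 0.736 (1,500 runs) was 80%, 81% and 85% unadjusted against 83%, 88% and 98% for ANCOVA.

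**Step 5, H4 against the pilot text.**

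| H4 effect | In survey content | In analysis list | Elsewhere in the documents |
|---|---|---|---|
| Beliefs | yes | B-IPQ, BMQ | – |
| Adherence | yes | MARS | – |
| PTSD symptoms | yes | PCL | – |
| Quality of life | no | no | Mini AQLQ in the cohort |
| Over-perception | no | no | AM2 devices in both pilot arms; symptom perception in DSMB reviews |

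The intervention arm guesses its peak flow before each reading, then sees the value, and has the unblinded device for the first 6 weeks. The control arm gets a blinded device, with no guessing procedure or duration stated.

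**The case against.** The pilot is a proof of concept, described in outline and awaiting separate IRB approval. A t-test in a randomised pilot is valid. Every gain above depends on r, which the documents do not give, and at r = 0.3 it all but disappears. The content of the baseline interview is not described, so the five scores may not be planned there. All of this stands, and it keeps the point modest.

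Four stronger readings are tempting but unsupported.
- A reader might infer that ignoring the balancing factors inflates false positives. Step 4 shows no inflation.
- A reader might infer that over-perception is not carried into the pilot at all. Both arms receive AM2 devices and the DSMB is to review symptom perception. What is missing is its place among the outcomes and analyses, and a matched procedure.
- A reader might infer that quality of life will not be collected. It is unlisted, but section 10 also pays for an end-of-study contact whose content is not described.
- A reader might infer that over-perception has to be measured after feedback ends. H4 claims correction and says nothing of persistence, so a post-feedback window is a design choice.

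Nor is the power statement shown to be false. It cannot be checked as written.

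**Conclusion.** The point holds in two parts. First, the analysis leaves available precision unused. At baseline correlations of 0.5 to 0.7 the detectable difference would fall from about 0.74 SD to 0.64–0.53 SD (0.66–0.55 SD in the worst case); at 0.3 the improvement is negligible. These sizes rest on an assumed two-sided 5% level, 30 analysed per arm, the assumed r and no session-group effect. Conservatism of the unadjusted test applies to the extent that an outcome is related to the balancing factors.

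Second, quality of life and over-perception are claimed in H4 but are not listed pilot outcomes and have no stated pilot analysis. This needs no assumption. Both parts should be settled in the pilot submission; neither affects the observational aims.

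**What to change.** In the pilot submission:

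1. Define the outcome as the 4-week follow-up score and name the scores analysed, since the BMQ has two subdomains, the ASI-3 three, and the B-IPQ covers five cognitive domains.
2. Analyse each by ANCOVA on its own baseline value plus age, sex and baseline PCL. For the PCL outcome, enter baseline PCL once. Collect the baseline at the pilot interview, or use the month-12 cohort value where available; the measures table schedules PCL, beliefs and MARS at month 12.
3. Add the Mini AQLQ to the pilot baseline and follow-up survey and analyse it the same way. Name the cohort's over-perception percentage as a pilot outcome, with the same guessing procedure and time window in both arms. Otherwise, remove these effects from H4's tested claims.
4. As a minor addition, state that power above 80% corresponds to a difference of about 0.74 SD or more with 30 analysed per arm.

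Items 1, 2 and 4 cost analysis wording and, at most, collection of the five instruments at an interview already scheduled. Item 3 costs a few minutes of interview time. If over-perception is kept, it also needs a defined AM2 window in both arms, using devices both arms already receive.

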The research staff, including project managers and research coordinators, will be trained to identify and report all adverse events, regardless of severity, as well as problems of data security, to the PI. Weekly study conference calls will involve the PI, Queens College site PI, project manager, and research coordinators. One of the main purposes of the calls will be to ensure patient and study safety and ensure compliance with monitoring and reporting. Toward these objectives, every meeting will include: (1) a report of the number and nature of all adverse events occurring during the previous week (monitoring study safety); (2) a discussion of the adverse events and development of a plan or change in study protocol to prevent similar or related adverse events, where possible (minimizing research-associated risk); (3) initiation of the process of reporting adverse events and unanticipated problems to the IRB, if they have not yet been reported already (adverse event reporting); (4) identification of breaches of confidentiality of participant data or problems of data

	Protocol Title:	Assessing Inflammatory and Behavioral Pathways Linking PTSD to Increased Asthma Morbidity in WTC Workers
	Principal Investigator Name/Contact Info:	[name], DrPH [contact]; [contact]
	Primary Contact Name/Contact Info	[name], MS [contact]; [contact]
	Date Revised:	07/25/16
	Study Number:	IF# 1896970; GCO# 16-0945

security, and discussion and development of plans to prevent problems of data security (ensuring data security). The protocol will be modified as needed to ensure patient safety and data security.

Safety Review Plan and Monitoring

- A. Safety reviews. During the observational study (considered low risk), a data safety monitoring board will not be employed. The PI will have overall responsibility for overseeing the safety of all study participants in this phase of the study. Locally, [name] will have primary responsibility for the safety of patients recruited at MSH. [name] (site PI) will have responsibility for patients recruited through the Queens site. During the pilot study (considered greater than minimal risk), a Data Safety Monitoring Board will oversee the safety of the study participants (see below).
- B. Annual review. The PI will review this protocol on a continuing basis for subject safety and include results of the review in the annual progress reports submitted to the IRB and NIOSH.
- C. Annual report. The annual report will include a list of adverse events.
- D. Content of annual report. The annual report will address: (1) whether adverse event rates are consistent with pre-study assumptions; (2) reason for dropouts from the study; and (3) whether all participants met entry criteria.

Data Safety and Monitoring Board (DSMB)

We will convene a DSMB to oversee participant safety for the pilot intervention proposed for Aim 4. (We will also submit a new IRB for this phase of the study.)

- A. Brief description of the DSMB: The board members will meet prior to implementation of the pilot RCT of the intervention to review the study protocol and measures to ensure that adequate protections and the plan to monitor for adverse events are adequate. They will then meet every 6 months after implementation of the pilot to review data, including the following elements: recruitment rate, study withdrawal, reasons for withdrawal, adverse events, impact of intervention on beliefs and behaviors, asthma symptom perception and symptoms of PTSD.
- B. Qualifications of DSMB members: The board will consist of a mental health expert, a pulmonologist, and a biostatistician. The board will not serve as co-investigators on the study. A DSMB chair will be identified and will convene the board yearly to review the study and accumulated data.
- C. Role and Responsibilities of the DSMB: The DSMB is an independent group advisory to the PI and is required to provide recommendations about starting, continuing, and stopping the study. In addition, the DSMB is asked to make recommendations, as appropriate, to the PI about:
 - Efficacy of the study intervention

 Mount Sinai	Protocol Title:	Assessing Inflammatory and Behavioral Pathways Linking PTSD to Increased Asthma Morbidity in WTC Workers
	Principal Investigator Name/Contact Info:	[name], DrPH [contact]; [contact]
	Primary Contact Name/Contact Info	[name], MS [contact]; [contact]
	Date Revised:	07/25/16
	Study Number:	IF# 1896970; GCO# 16-0945

- Benefit/risk ratio of procedures and participant burden
- Selection, recruitment, and retention of participants
- Adherence to protocol requirements
- Completeness, quality, and analysis of measurements
- Amendments to the study protocol and consent forms
- Participant safety
- Notification of and referral for abnormal findings

The DSMB will monitor patient safety, consider new scientific or therapeutic developments that could impact safety or trial ethics, and make recommendations to continue, terminate, or modify the trial based on interim analyses. The DSMB will specifically review: 1) hospitalization and mortality rates; 2) study disenrollment unrelated to death; 3) and any participant and healthcare provider concerns. The DSMB may recommend stopping the trial if there is clear evidence of harm or overwhelming benefit. Adverse events will include disruption of previously established regular care such that the participant's health is jeopardized or excessive burden created by the time required to participate in the study. The DSMB can recommend changes in study protocol or termination of the study if it concludes the study design causes disruptions in patient-provider continuity which jeopardized the health of the study subject or if the study imposes excessive burden on participants. Finally the DSMB, at the request of the sponsor, will review accrual and evaluate study progress towards meeting recruitment targets.

The DSMB will review safety and data information yearly. Should a temporary or permanent suspension of the study occur, in addition to the PPHS, we will report this to NIOSH.

j) Withdrawal of Subjects

Participants may choose to withdraw from the study at any time without any penalty. If participants decide to withdraw from the study, they need to contact the PI or research staff. If participants wish to withdraw their permission for use and disclosure of any of their protected health information for research, they must do so in writing to the PI at the address on the consent.

5) Risks to Subjects

The proposed study will use survey instruments and interventions that are similar to those used by us and other investigators previously. We do not anticipate any significant physical, psychological, or social risk to the study participants. Research subjects could become fatigued during the interview. To limit this risk we will provide multiple opportunities for breaks. Distress may also result from questions relating to depressive

 Mount Sinai	Protocol Title:	Assessing Inflammatory and Behavioral Pathways Linking PTSD to Increased Asthma Morbidity in WTC Workers
	Principal Investigator Name/Contact Info:	[name], DrPH [contact]; [contact]
	Primary Contact Name/Contact Info	[name], MS [contact]; [contact]
	Date Revised:	07/25/16
